Premedication was administered with intravenous midazolam (0.02 mg/kg) as a premedication at the reception area of operating theater and then transferred to the operating room. In the operating room, standard monitoring, including electrocardiography, noninvasive arterial pressure measurements, and pulse oximetry was placed. The level of NMB was monitored using acceleromyography (TOF-Watch® SX, Organon Ireland Ltd., a subsidiary of Merck & Co., Inc., Swords, Co. Dublin, Ireland) at the adductor pollicis muscle. The TOF ratio was recorded for each patient every 5 min during the operation. The TOFwatch was calibrated in each patient before performing the measurements. The stimulation current was set to 30 mA and the TOF-watch SX was calibrated in the calibration 1 mode. During induction of anesthesia, patients received propofol (2 mg/kg) and alfentanil and the Igel[™] (Intersurgical Ltd, Wokingham, UK) was inserted after the administration of 0.6 mg/kg rocuronium in both groups. Anesthesia was maintained with desflurane while monitoring the bispectral index (A-2000 BISTM monitor; Aspect Medical Systems, Inc., Natick, MA, USA) between 40-60. A bolus dose of intravenous rocuronium (5-10 mg) was used to maintain moderate (moderate NMB group, TOF count of 1 or 2) or deep (deep NMB group, TOF count of 0 with PTC of 2) NMB if needed. At the end of the operation, the surgeon rated the endoscopic surgical condition on a 5-point scale (1 = extremely poor, 2 = poor, 3 =

acceptable, 4 = good, 5= optimal, Table 1) [9]. Patients in moderate NMB group are reversed with 2 mg/kg sugammadex at a TOF count of 1 or 2 (group A) and patients in the deep NMB group are reversed with 4 mg/kg sugammadex at PTC of 2 (group B). Patients were extubated when spontaneous ventilation of the patient was adequate. After the surgery, patients were transferred to the post-anesthesia care unit (PACU)

Postoperative residual curarization (PORC, TOF ratio < 0.9) is recorded if it occurred. Patients were evaluated every 15 min using the modified Aldrete scoring system until ready for discharge from the PACU and the criterion used for patient discharge was the achievement of a modified Aldrete score of 9 [10]. Respiratory complication such as desaturation (SpO2 < 90%) or respiratory depression (RR < 8) and other adverse events including postoperative nausea and/or vomiting (PONV) were recorded during PACU stay.

Outcome measurement

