Primary outcome was the endoscopic surgical condition that was evaluated right after the operation by the surgeon (Table 1), who was blinded to the group assignment. Secondary outcomes were recovery profiles including the postoperative residual curarization (PORC, TOF ratio < 0.9), respiratory complications, recovery time (PACU discharge, a modified Aldrete score of 9) and other postoperative adverse events.

Sample size

The sample size was calculated based on the preliminary data using G*Power 3.1.2 (Heinrich-Heine University, Düsseldorf, Germany). The proportion of optimal endoscopic surgical condition (score 5) during TURB was 30 % after the use of moderate NMB (n = 10) and 30% increase of optimal endoscopic surgical condition by deep NMB was considered to

be clinically significant. Fifty four (54) patients per group was calculated with $\alpha = 0.05$ and $\beta = 0.2$, allowing for a 10 % drop-out rate.

Statistical analysis

Statistical analysis is performed using SPSS 21 (SPSS Inc., Chicago, IL, USA) and the test of normal distribution was assessed with the Shapiro–Wilk test. Chi-square test or Fisher's exact test was used for the analysis of incidence variables (gender, ASA physical class, additional rocuronium, surgical condition score, PORC, respiratory complications and other adverse events). Student's t test is used to compare normally distributed continuous variables (age, weight, height, BMI, operation time, anesthesia time, propofol, alfentanil, rocuronium, and recovery time). All values presented are number of patients (%) or mean (SD). A p values < 0.05 were considered to indicate statistical significance.

Score	Surgical condition	
1.	Extremely poor conditions	The surgeon is unable to work because of coughing or
		because of the inability to obtain a endoscopic view
		because of inadequate muscle relaxation. Additional
		neuromuscular blocking agents must be given
2.	Poor conditions	There is a endoscopic view but the surgeon is severely
		hampered by inadequate muscle relaxation with
		continuous muscle contractions, movements, or both
		with the hazard of tissue damage. Additional
		neuromuscular blocking agents must be given
3.	Acceptable conditions	There is a wide endoscopic view but bladder
		contractions, movements, or both occur regularly
		causing some interference with the surgeon's work.
		There is the need for additional neuromuscular
		blocking agents to prevent deterioration

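### Must recovery time leave the t-test list because the Aldrete score is taken only every 15 minutes?

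*SAP*

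**What the plan says.** The Outcome measurement section lists, among several secondary recovery profiles, "recovery time (PACU discharge, a modified Aldrete score of 9"). The Anesthesia section describes how the score is obtained: "Patients were evaluated every 15 min using the modified Aldrete scoring system until ready for discharge from the PACU". Under the same section, a patient may leave the unit once the score reaches 9.

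The Statistical analysis section states that "the test of normal distribution was assessed with the Shapiro–Wilk test". It then says that Student's "t test is used to compare normally distributed continuous variables (age, weight, height, BMI, operation time, anesthesia time, propofol, alfentanil, rocuronium, and recovery time"), and on presentation: "All values presented are number of patients (%) or mean (SD"). The significance rule is "A p values < 0.05 were considered to indicate statistical significance".

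The only tests named are chi-square, Fisher's exact and Student's t. The SAP does not say what follows if a listed variable fails Shapiro–Wilk. It also does not say from what moment recovery time is counted, or whether it is read at the scoring checks or from the clock at discharge.

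**The concern.** Read together, these passages seem to defeat each other. If the score of 9 can be seen only at a 15-minute check, recovery time can equal only 15, 30, 45 minutes and so on. Such a variable is not normal, and a normality test on about 50 patients will detect that. Yet the plan lists it in advance as normally distributed and names no alternative.

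The analyst would then either apply a t test after its stated condition had failed, or choose another test after seeing the data. Recovery time is the only continuous variable among the secondary outcomes, so this is where an unplanned choice could matter. If the times are also right-skewed, as discharge times may be, the mean (SD) describes them poorly and the t test may lose power to a rank test.

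**Working it through.** **Inputs.** From the SAP: 54 patients per group, 10% drop-out, α = 0.05 (taken as two-sided), β = 0.2, and scoring every 15 minutes. The SAP gives no mean, spread or shape for recovery time. Its preliminary data concern only the surgical condition, where the rate of optimal scores "was 30 % after the use of moderate NMB (n = 10"). Every recovery-time distribution below is therefore an assumption.

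**The plan's own figure.** For 30% versus 60%, the uncorrected formula gives n′ = [1.96·√(2·0.45·0.55) + 0.84·√(0.3·0.7 + 0.6·0.4)]² / 0.30² ≈ 42. The continuity correction gives n = (42/4)·[1 + √(1 + 4/(42·0.30))]² ≈ 48.4, so 49. Then 49 × 1.10 = 53.9, so 54, which matches the plan. This figure does not depend on recovery time. It sets the range of 49 to 54 per group used below.

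**Check 1: exact 15-minute grid.** True times have mean 45 min and are rounded up to the next multiple of 15. The shift for power is 0.6 SD, with 2,000 runs per setting. Results for 49 per group:

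| Underlying time | SD (min) | Distinct values per group | Shapiro–Wilk rejects | t test type I error | Power, t | Power, Mann–Whitney |
|---|---|---|---|---|---|---|
| Normal | 5 | 2.1 | 100% | 5.4% | 65.9% | 65.2% |
| Normal | 10 | 4.1 | 100% | 4.6% | 75.3% | 74.5% |
| Normal | 15 | 5.4 | 100% | 4.8% | 81.1% | 79.6% |
| Normal | 30 | 7.7 | 98% | 5.7% | 82.5% | 81.1% |
| Lognormal | 10 | 4.2 | 100% | 4.1% | 75.6% | 76.5% |
| Lognormal | 15 | 5.3 | 100% | 4.7% | 81.8% | 85.3% |
| Lognormal | 30 | 8.4 | 100% | 4.8% | 83.1% | 97.1% |

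Over all settings with 49 or 54 per group, the t test's type I error lies between 4.1% and 5.7%. Shapiro–Wilk detects the grid almost every time, but the comparison of means is not disturbed by it. The rank test is level or slightly behind for symmetric times. It is clearly ahead only under strong skew: 97.1 − 83.1 = 14.0 points in the last row.

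**Check 2: skew by degree.** The grid, 49 per group, and a shift of 0.58 SD on the log scale. Power for t versus Mann–Whitney is 72% vs 72% (log-SD 0.4), 73% vs 76% (0.6) and 68% vs 78% (0.8). The gain is therefore 0, 3 and 10 points.

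**Check 3: is the grid given?** The SAP fixes how often the score is taken, not how recovery time is written down, and its definition names PACU discharge. Suppose that a variable delay separates the check from the recorded discharge (assumed uniform over 0–15 min, or normal with SD 3 or 5 min). With 49 per group and normal underlying times, Shapiro–Wilk rejection falls from 100% to:

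- SD 15 min: 5% to 16%
- SD 10 min: 8% to 46%
- SD 6 min: 29% to 98%

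For lognormal times it stays at 64% to 99%, but skew causes that rather than the scoring interval. The t test's type I error again stays at about 4% to 6%. With normal times of SD 6 min and a delay of SD 3 min, power is 59.4% for the t test and 49.9% for Mann–Whitney, a loss of 59.4 − 49.9 = 9.5 points for the rank test.

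**The case for a change.** The best case for a change is that the plan sets up a normality check with only one way out. If the outcome is read at the scoring checks, failure is close to certain, even for times that are exactly normal underneath. Without the grid, normal data fail only 4% to 6% of the time. Naming a fallback would cost one sentence and would close off a choice made after unblinding. If the times are strongly skewed, the rank test is materially more powerful and a median describes them better.

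Part of this stands. The fallback is missing, and Shapiro–Wilk would very probably reject gridded or skewed times.

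The step from there to a defective analysis does not stand. Exact grid recording is inferred and is not stated in the plan. A Shapiro–Wilk rejection of coarsely recorded data does not show that a t test on about 50 per group misleads, and here its error rate is right. Nor is the plan without a test: recovery time is listed by name, so following the list gives one prespecified comparison. An analyst who moved to a rank test would be making a visible departure. The claim that a rank test costs almost nothing holds on the exact grid with symmetric times, but not once recorded times depart from the grid.

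**Conclusion.** No change to the plan is needed. The quoted passages do leave open what happens when a continuous variable fails the normality check. For recovery time, though, the analysis as written gives a valid comparison: type I error is about 4% to 6% in every setting examined. Replacing the t test with Mann–Whitney is a trade-off. The rank test gains about 10 to 14 points of power if times are strongly skewed, roughly nothing if they are mildly skewed or symmetric on the grid, and can lose up to 9.5 points if they are symmetric and the grid is blurred. Reasonable statisticians could choose either, and the mean difference in PACU time has the merit of direct interpretation. If the times prove skewed, an analyst can show a median and a rank test beside the planned result without altering it.

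The outcome is secondary and did not determine the sample size, so the primary conclusion is unaffected. This verdict rests on about 49 to 54 patients per group with equal allocation, two-sided testing at 0.05, and assumed distributions (a mean of 45 min and SDs of 5 to 30 min on the exact grid, SDs of 6 to 15 min with a blurred grid, log-SDs of 0.4 to 0.8). Much smaller groups or far heavier tails were not examined.
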